
Security monitoring and assessments
	
For the application of the FINDRISC screening questionnaire it is required to take non-invasive anthropometric measurements and to establish the status of prediabetes or undiagnosed diabetes, blood samples are required. The safety follow-up to these procedures will be carried out in accordance with current standards.
	

Title

Comparative effectiveness of point-of-care glycosylated hemoglobin measurement (POC-A1c), vs. the current standard based on oral glucose tolerance test, for the early detection of Type 2 Diabetes Mellitus (T2DM) in Colombia. **EDDIT-1 STUDY**

Theoretical framework

Type 2 diabetes mellitus (T2DM) is a growing public health problem in the world and in Colombia. In 2020, this pathology was considered the ninth cause of mortality in the world according to the global burden of disease (GBD) with more than 1 million deaths per year directly caused by diabetes (1). In Latin America, 1 in 3 adults living with diabetes are undiagnosed and in Colombia the behavior is similar, as reports from the High-Cost Account indicate that 3 out of every 100 Colombians have diabetes mellitus. However, the Ministry of Health and Social Protection estimates that the number is much higher and one in 10 people in Colombia suffers from this disease, this because at least half of the population does not know they have this pathology.

To reduce the gap of undiagnosed people, it is necessary to design and implement strategies for early detection of T2DM. The Berlin Declaration (2), published in October 2016 and supported by the IDF as well as other organizations, has identified early detection as a priority line and has set a goal for achieving this priority (2). This statement proposes to increase by 50% the number of people taking a risk test for T2DM and by 50% the number of high-risk people receiving a diagnostic test for T2DM.

According to this, it is important to consider the diagnostic criteria set forth by the American Diabetes Association (ADA) in 2022 (3):

- Fasting blood glucose (fasting - absence of caloric intake for at least 8 continuous hours) ≥ 126 mg/dL

or

- Oral Glucose Tolerance Test (according to WHO guidelines with an equivalent of 75 g of anhydrous glucose dissolved in water) at 2 hours: ≥ 200 mg/dL

or

- HBA1C $\geq 6.5\%$

or

- In patients with classic symptoms of hyperglycaemia or hyperglycaemia crisis, or random glycaemia ≥ 200 mg/dL

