Follow-up of withdrawn subjects

Once the subject expresses his intention to withdraw, the follow-up will be terminated.

Criteria for the interruption of the study.

Since the intervention is not therapeutic and the technical conditions for performing laboratory tests are standardized, no a priori termination criteria are established.

Interventions

Description of interventions

The FINDRISC (applied in Pre-Screening activity) will be verified; for this it is necessary to take anthropometrics well as non-invasive measurements. Additionally, to establish the diagnosis of prediabetes or undiagnosed diabetes, invasive activities such as blood sampling are required.

Non-invasive measurements

Body weight (at 0.1 g precision) in lightweight underwear, without footwear, will be recorded at the screening visit as well as height (at 0.5 cm precision), that is, both measurements will be obtained at the beginning of the study. The waist and hip circumference will be taken twice, then the average of both measurements will be made.

Biochemical measurements

The PGTT will be carried out according to the standards of the allied laboratory or of preference by the patient, and under the local regulations of the country with the recommendations of the WHO. Ideally, the loading solution should contain 75 g of anhydride glucose and 1.6 g of citric acid, the first sample of glycemia will be obtained after 8 - 12 hours of fasting and the second sample will be obtained 2 hours after glucose loading. All this according to the recommendations described by the WHO.

PoC-A1c will be measured at the screening site using validated equipment that complies with international standards. Kits and processing methods will be ensured to be certified by the NGSP and standardized with the DCCT assay. The POC-A1c test shall be considered impaired for any value equal to or greater than 5.7% (3).

Enumeration of the participant

The enumeration of patients will be sequential since it is performed in a single center.

Allocation of the intervention

Once the participant has accepted and signed the informed consent, the doctor will verify the FINDRISC questionnaire previously applied in prescreening activities), as well as inclusion and exclusion criteria and random assignment will be carried out by the research team.

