The random allocation sequence will be automatically generated through the platform intended for this purpose. A member of the research team will record the group to which the participant was assigned on the data logging platform.

Instructions to the patient

In Pre-Screening activities, a member of the research team must give the participant a flyer with educational information about healthy lifestyles, regardless of the participant's score. In addition to all participants who enter the study, they will be given an order for the realization of the PWG with the relevant indications for the taking of the sample and the flyer mentioned above.

In this documentation must be the sequence number that was assigned to the patient, as well as their identification number so that when they go to the sampling site (CAIMED allied laboratory/Laboratory of their preference) they are identified as a participant in the study. This will make it possible to monitor which participants have already completed the GGP. 30 days after applying the screening questionnaire or the completion of the GTT, the follow-up call is made.

The script is as follows:

"Good morning / good afternoon / good evening, Madam/Sir (name of the subject). My name is (Contributor Name) I am (Position) We are calling you on behalf of the diabetes early detection study. As you recall, on the day (date

	
Effectiveness comparison of the hemoglobin measurement glycosylated at the point of care (POC-A1c), vs the standard current based on tolerance test oral to glucose, for the detection early of Diabetes Mellitus guy 2 (DM2) in Colombia. EDDIT-1 STUDY
	
Version: 3.0 Date: February 15, 2022

---	--	---

of inclusion in the study) you participated in the site (inclusion site to the study) in the diabetes study. I would like to know if you had the sugar test indicated by the doctor (corresponding to the day of completion of window 1 for the OGTT).

(Wait for a reply)

If the patient replies that the test was performed, the date and result should be confirmed and ask: "Could you please send us a photo or any proof of the report? Finally, the call should end like this: "Thank you very much Ms./Mr. (name of the subject). Remember to consult your doctor or your EPS to initiate timely management of the disease (in case it is impaired) or monitor the risk at least annually."

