If the answer is I have not taken the test: Could you please tell us why you have not taken the sugar test? Wait for a response, and document it, end the call like this: "Remember that we will call you in 2 months again to confirm if the test was done."

**The answers are recorded by the platform and will be analyzed qualitatively by the researchers.*

Scheduling of study visits (schedule)

Responsible	Prescreening	Visit 1	Phone Call 1 (30 days ± 3 days)	Phone Call 2 (90 days ± 3 days)	Phone Call 3 (30 days after reporting to the center ± 3 days, if applicable)
Doctor Bacteriologist Research Assistant	– Conferences of application of FindRisc as risk screening				
Doctor		Explanation of the study, its procedures and obtaining the consent informed. Review of eligibility criteria.			
Research Assistant		VERIFICATION of FINDRISC, Randomization and data processing on the platform			
Research Assistant		Data processing on the platform to the corresponding group			
Laboratory		Implementation of POC-A1c			

Effectiveness comparison of the hemoglobin measurement glycosylated at the point of care (POC-A1c), vs the standard current based on tolerance test oral to glucose, for the detection early of Diabetes Mellitus guy 2 (DM2) in Colombia. **EDDIT-1 STUDY**

Version: 3.0
Date: February 15, 2022

CRS			Follow-up call 30 days after the PGT request.	Follow-up call - 30-90 days after admission to the study in patients not attending OGTT.	Verification call 30 days from the report of the result of the requested test. To those who present an impaired OGMP and have requested a control doctor.

Bias Control

- **Bias derived from the randomization process:** it is carried out through the Office - Excel platform by means of algorithms for the generation of random numbers and their assignment to the specific group, by means of a simple impaired randomization; in order to maintain the masking of the assignment, a number (1-2) will be assigned to classify the intervention and its comparator, keeping this hidden from most researchers.
- **Bias due to deviations from planned interventions:** from study design, with simple randomization, the subject who has received a group assignment cannot move on to the other.
- **Bias due to the lack of outcome data:** The number of stratified lost data of intervened versus non-intervened will be evaluated, if it exceeds 5% analysis and data imputation will be made.

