According to the described methodology, the significance level for the primary objective is 0.05.

Procedure to Explain Missing Data

Any deviation from the statistical plan will be discussed with all authors for approval.

Selection of subjects to be included in the analyses

The final analysis will include all individuals with complete data.

Ethical considerations

The research group will submit to the Ethics Committee for consideration all required documentation from the study, explain the risks and benefits and ask for their written consent. Each participant shall have the right to leave the study when he/she so arranges. The study will follow the Good Clinical Practice regulations of the Helsinki Declaration. An adverse effects data collection sheet will be used, it is estimated that possible adverse effects will be related to taking capillary puncture for POCA1C (puncture site infection and pain or dizziness/vomiting).

Data management and record keeping

Data management and record keeping will be carried out in accordance with the current procedures of MetricsMed and a specific parameterization is contemplated for the implementation of this project.

Financing and insurance (budget and schedule of activities)

	
Effectiveness comparison of the hemoglobin measurement glycosylated at the point of care (POC-A1c), vs the standard current based on tolerance test oral to glucose, for the detection early of Diabetes Mellitus guy 2 (DM2) in Colombia. EDDIT-1 STUDY
	
Version: 3.0 Date: February 15, 2022

---	--	---

See annex budget 5.

Publication Policy

The publications will be based on data from the center, analyzed according to the protocol. Researchers undertake not to publish data obtained in a centre or in a small group of centers before the main publication (or updates of the same), unless they are formally accepted by all other researchers. Authorship, order of authors, publications and results of the study shall be determined in accordance with the authors according to international standards for publications.

[figure not shown]
Annexes

1. Flow of interventions and procedures
2. Informed consent
3. FINDRISC Questionnaire
4. Table of variables
5. Schedule of activities – Budget

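### No contact after Visit 1 is described as asking about adverse effects, so delayed puncture events and events at the off-site OGTT are likely to be under-recorded

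*Combined protocol and SAP*

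**What the plan says.** Under Ethical considerations the protocol commits to a recording tool: "An adverse effects data collection sheet will be used". It then names what it expects: "it is estimated that possible adverse effects will be related to taking capillary puncture for POCA1C (puncture site infection and pain or dizziness/vomiting". It gives no collection window, responsible role or question to be asked. The Protocol Synopsis (Security monitoring and assessments) adds a general undertaking about the measurements and blood samples: "The safety follow-up to these procedures will be carried out in accordance with current standards". It names no contact at which this happens.

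After Visit 1 the participant is reached only by phone. The script under Instructions to the patient opens with "I would like to know if you had the sugar test indicated by the doctor". One branch reads "If the patient replies that the test was performed, the date and result should be confirmed and ask" and goes on to request proof of the report. The other asks "Could you please tell us why you have not taken the sugar test". In the visit schedule, Call 1 is described as "Follow-up call 30 days after the PGT request".

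The OGTT is ordered for everyone randomised and is done at an allied laboratory or one the participant chooses (Study procedures). Under Biochemical measurements it involves an 8 to 12 hour fast, a first sample and a 75 g glucose load, and "the second sample will be obtained 2 hours after glucose loading".

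**The concern.** The plan names an event that tends to appear late and says it will collect such events, but describes no later moment at which anyone asks. It also ties the expected effects to the finger-prick alone. The OGTT, which every participant is sent to have elsewhere, is not listed as a possible source, and no route is described for an outside laboratory to report an event to the study team.

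What is at stake is how completely safety events are ascertained. Events not asked about during the trial cannot be recovered at analysis. A low count on the sheet could then mean few events or few questions, and the reader could not tell which. This matters somewhat for the OGTT because the strategy under test is meant to send more people to it.

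**Working it through.** **1. The plan's own figures (Sample size).** Inputs: 60% attendance in A, 50% in B, 80% power, two-sided 0.05.
- Standard two-proportion formula without continuity correction: 388 per arm, 776 in total, close to the stated 784.
- Maximum-variance form: (1.960 + 0.842)² × 0.5 / 0.10² = 392.4, which matches the stated 392 per arm.
- Adjustment: 392 × 1.3 = 509.6, so 510 in A; 510 + 392 = 902. The stated totals reproduce.

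**2. Number of procedures followed by no described adverse-effect question.**
- Capillary punctures: 510 (group A only).
- Expected OGTTs: 510 × 0.60 = 306 in A; 392 × 0.50 = 196 in B; 306 + 196 = 502.

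**3. What each later contact is described as covering** (Synopsis, Study procedures, Instructions to the patient, visit schedule).

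| Contact | Who | Described content | Adverse-effect question |
|---|---|---|---|
| Call 1, 30 ± 3 days | All randomised | OGTT done or not; date, result and proof; reason if not done | None in the printed script |
| Call 2, 90 ± 3 days | Those who had not attended the OGTT | Whether the test has since been done | None stated; no wording printed |
| Call 3, 30 days after the test or its report (the sections differ) | Attenders with an impaired result | Whether control of the disease has begun | None stated; no wording printed |

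For a participant who attends before Call 1 with a normal result, Call 1 is the last contact.

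**4. Downstream of the calls.** Annex 4 covers demographics, anthropometry, family history, risk factors, biochemistry, the risk score and diagnosis, with no adverse-effect variable. Description of statistical methods contains no adverse-effect summary, and Bias Control limits the analysis to what is proposed there.

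**5. Possible size.** The documents give no event rate, so a range is assumed for illustration only.

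| Assumed rate | Events in 510 punctures | Events in 502 OGTTs |
|---|---|---|
| 0.1% | 510 × 0.001 = 0.5 | 502 × 0.001 = 0.5 |
| 0.5% | 510 × 0.005 = 2.6 | 502 × 0.005 = 2.5 |
| 1% | 510 × 0.01 = 5.1 | 502 × 0.01 = 5.0 |

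At such rates a handful of events is in question, so missing even a few would change the count materially.

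**The case against.** A reader might infer that delayed puncture events and all OGTT events will go unrecorded. The documents do not support that. The sheet has no stated end date or place, so an event that a participant volunteers can be entered. Non-attenders are asked an open question about their reason, and the answer is documented; a bad experience could surface there. The supportable statement is that events are not systematically asked about.

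A reader might also infer that the trial will report no infections or present the strategy as free of harm. No safety endpoint, rate, comparison or conclusion is planned, so this is at most a risk in later reporting.

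Three further limits stand. The printed script is worded for the 30-day call; for Calls 2 and 3 the point rests on their stated purpose. The adverse-effects sheet, the consent form and the Annex 1 flow figure are not in the available text, and the general undertaking on safety follow-up refers to standards that cannot be inspected, so any of these might contain a prompt. And of the listed effects, pain and dizziness or vomiting could be seen at Visit 1; infection is the one that mainly depends on later contact.

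It can also be argued that the OGTT belongs to recommended practice in both arms, is done under laboratory standards, and need not be treated as a study procedure. That is a defensible reason for emphasising the finger-prick. It does not explain why calls already made about the OGTT omit a question on how it went.

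Finally, a finger-prick question asked only in group A would make call content differ by arm inside the 90-day outcome window of an open-label trial. That is a valid objection to an arm-specific question, and the remedy must avoid it.

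**Conclusion.** The point holds as a gap in solicitation. The plan expects a delayed adverse effect and provides a sheet, but no contact after Visit 1 is described as asking, and no variable or summary is set up to receive the answer. Up to 510 punctures and about 502 OGTTs are affected, the latter if attendance matches the planning rates of 60% and 50%. Under-recording is likely but cannot be quantified, because no event rates are given.

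The conclusion assumes that an infection usually becomes apparent after the participant leaves the site, and that the sheet and consent form, which were not available, do not already schedule a later enquiry. The primary endpoint, sample size and attendance analysis are unaffected. The procedures are routine, so this is a low-cost improvement to safety ascertainment and not a threat to the trial's main result.

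**What to change.** - Add one neutral question to Calls 1 and 2, worded identically in both arms and asked after the attendance questions. For example: *Have you had any health problem since the study visit, or during or after the sugar test?* Call 1 covers everyone; Call 2 covers those who had not attended by then, and so their later OGTTs.
- Record the answer on the existing adverse-effects sheet with the procedure concerned and the date, and add an adverse-effect variable to Annex 4.
- In Ethical considerations, list the OGTT as a possible source of adverse effects.
- Add a line to Description of statistical methods: report OGTT events by arm and puncture events descriptively for group A only (group B has no puncture), stating that they were elicited by recall at 30 or 90 days.

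Cost: slightly longer calls, a line on an existing form and one more variable. No new visit or procedure is needed. Recall of minor events at 30 or 90 days will be imperfect. The common wording, and its position after the attendance questions, keep call content the same across arms during the outcome window. If the sheet or consent form already contains such a prompt, the change reduces to stating it in the protocol and aligning the script.

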Annex 1: Flow of interventions and procedures

Annex 2: Informed consent

View attachment

Annex 3: FINDRISC Questionnaire

FINDRISC QUESTIONNAIRE

1. Age
 - <45 years old 0 points
 - 45-54 years old 2 points
 - 55-64 years old 3 points
 - >65 years old 4 points
2. IMC (kg/m²)
 - <25 0 points
 - 25-30 1 point
 - >30 3 points
3. Waist perimeter

Men	Women
<94 cm	<80 cm 0 points
94-102 cm	80-88 cm 3 points
>102 cm	>88 cm 4 points
4. Do they perform at least 30 minutes of physical activity at work on free time?
 - YES 0 points
 - NO 2 points
5. How often do they eat fruits or vegetables?
 - Every day 0 points
 - Not every day 1 point
6. Do they have high-blood pressure or take daily medication for hypertension?
 - NO 0 points
 - YES 2 points
7. Have they ever had high glucose levels?
 - NO 0 points
 - YES 5 points
8. Has any of their family members or relatives ever been diagnosed with diabetes?
 - NO 0 points
 - YES... grandparents, uncles, aunts, cousins... 3 points
 - YES ... parents, siblings, children 5 points

Taken from ScienceDirect, Spanish clinical magazine, Volume 210, Issue 9, October 2010, pages 448-453

Annex 4: Table of variables.

Variable	Conceptual Definition	Operational Definition	Measurement scale
Demographics			
Identification	Citizenship Card Number	Integers	Discrete Quantitative Ratio
Health Coverage	Health care provider according to Colombian legislation, can be subsidized, contributory according to the social stratum of the person.	EPS –S (Subsidized) EPS –C (Contributory) Other (Exception Regime)	Qualitative Dichotomous
Gender	Sex of the patient	Male Female	Qualitative Nominal Dichotomous
Date of Birth	Main facts about the birth of a person according to the data issued in the official record or document.	Day Month Year	Quantitative Discrete
Marital Status	Permanent status of a natural (natural) person in relation to his or her personal circumstance and legislation.	Single Married Widower Divorced Free Union Separate	Qualitative Dichotomous Nominal
Last grade of schooling obtained	Degree of instruction by the school, parents, or caregiver.	Primary Secondary Technical Technology University Without studies	Qualitative Dichotomous Nominal
Employment Status	Set of activities that are carried out with the aim of reaching a goal, solving a problem or producing goods and services to meet human needs. Are you? Doing any paid (paid) work right now?	Yes No	Qualitative Dichotomous Nominal
Socio-economic stratum	Classification into strata of residential properties that must receive public services	1 2 3 4 5 6	Qualitative Ordinal
Anthropometric (non-invasive) measurements			
Weight	Magnitude in kilograms of a subject	Measured in kilograms (Kg)	Continuous Quantitative of Reason
Size	Height in centimeters of a subject	Measured in centimeters (Cm) with conversion to meters (mt)	Continuous Quantitative of Reason

Waist	Circumference measurement performed 1cm below the navel to determine abdominal obesity and expressed in centimeters.		Measured in centimeters (Cm)	Continuous Quantitative of Reason
BMI	Weight in kilograms divided over the size in meters squared		Measured in kg/m ²	Continuous Quantitative of Reason
Family History				
Family member over 18 years of age with Diagnosis of DM	History of Diabetes Mellitus in direct family	Have any of your close relatives or other relatives been diagnosed with diabetes?	No Yes: grandparents, aunt, uncle, first cousin (not parents, siblings or children) Yes: parents or siblings	Nominal qualitative
Risk factors				
Diabetes Mellitus	Disease where there is excess blood sugar (glucose) from Pancreatic failure (Endocrine organ)	Has a doctor, nurse, or other health professional ever told you that you have or had Diabetes or high blood sugar?	Yes No	Dichotomous qualitative
Treatment for the Hipertension	Medicine that regulates the blood pressure	Do you take the medication for hypertension regularly?	Yes No	Dichotomous qualitative
Physical activity	Any body movement produced by skeletal muscles, with the consequent consumption of energy.	Usually perform at least 30 minutes of physical activity, at work and / or in free time?	Yes No	Dichotomous qualitative
Consumption of fruits and vegetables	Feeding from fruits and vegetables	How often do you eat vegetables or fruits?	Every day Not every day	Dichotomous qualitative
Biochemical Variables				
POC-A1c	Glycosylated Hemoglobin at Point of Care	PoC-A1c result	% or mmol/mol	Quantitative of Continuous Ratio

OGTT	Oral glucose tolerance test.	Result of the OGTT	mg / dl	Quantitative of Continuous Ratio
Date of Take OGTT	Date of performing the test	Date of OGTT Test	day/month/year	Discrete Quantitative
Risk calculation				

		Comparative effectiveness of point-of-care glycosylated hemoglobin measurement (POC-A1c), vs. the current standard based on oral glucose tolerance test, for the early detection of Type 2 Diabetes Mellitus (T2DM) in Colombia. EDDIT-1 STUDY		Version: 3.0 Date: February 15, 2022	
Screening result by FINDRISC	Scale to detect patients at higher risk of developing T2DM in the next ten years	Final result of FINDRISC	Points. Integer numeric value (discrete)	Quantitative Discrete	
Final Diagnosis					
Patient presents Diabetes	Disease where there is excess blood sugar (glucose) from pancreatic failure (endocrine organ) as of performed diagnosis test.	Result according to OGTT or POC A1C and guidelines of clinical practice guidelines -, ADA	Yes No	Qualitative Dichotomous	

